## **J 5        Drugs that may Prolong QT Interval**

The drugs listed in this section are taken from information provided by [The Arizona Center for Education and Research on Therapeutics on the CredibleMeds® website](#):

<https://www.crediblemeds.org>. The website categorises drugs based on the risk of inducing TdP.

During screening, the drugs that patients are currently receiving (prescribed and non-prescription) should be checked against the Arizona Center website above. In addition, drugs intended for use following study intervention initiation should be checked against the website.

### **J 5.1        Drugs with a Known Risk of TdP**

The following drugs prolong QT interval and are clearly associated with a known risk of TdP even when taken as recommended. These drugs must have been discontinued prior to the start of administration of study intervention, in accordance with guidance provided in [Table J4](#) and should not be co-administered with savolitinib or osimertinib and for a period of two weeks after discontinuing study intervention.

The list of drugs may not be exhaustive and is subject to change as new information becomes available. As such, investigators are recommended to search the Arizona Center website to confirm the most up to date information. Recommended withdrawal periods following cessation of treatment with these agents are provided in [Table J4](#).

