Drugs prolonging QT interval	
The concomitant administration of drugs known to prolong QT interval is restricted unless considered essential due to patient management, in which case, patients should be closely monitored with more frequent ECGs. Additional guidance on drugs known to prolong QT interval is provided in Appendix J.
 
The following drugs are known to prolong QT interval or induce Torsades de Pointes and should not be combined with osimertinib:
 
Clarithromycin, droperidol, erythromycin, procainamide, cisapride, disopyramide, dofetilide, domperidone, ibutilide, quinidine, sotalol, sparfloxacin, thioridazine, bepridil, chlorpromazine, halofantrine, haloperidol, mesoridazine, levomethadyl, methadone, pimozide, arsenic trioxide, pentamidine, amiodarone, chloroquine (Appendix J).

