**Table 6 Restricted Medications**

Medication/class of drug	Usage (including limits for duration permitted and special situations in which it's allowed)
Drugs that may possibly prolong QT interval	
The use of the following drugs is permitted (notwithstanding other exclusions and restrictions) provided the patient has been stable on therapy for the periods indicated:
 
Alfuzosin, chloral hydrate, ciprofloxacin, dolasetron, foscarnet, galantamine, gemifloxacin, isradipine, ketoconazole, levofloxacin, mexiletine, nifedipine, octreotide, ofloxacin, ondansetron, quetiapine, ranolazine, telithromycin, tizanidine, vardenafil, venlafaxine, ziprasidone.
 
Amantadine, amitriptyline, amoxapine, clozapine, doxepin, felbamate, flecainide, fluconazole, fosphenytoin, gatifloxacin, granisetron, imipramine, indapamide, lithium, moexipril/HCTZ, moxifloxacin, risperidone, roxithromycin, sertraline, trimethoprim-sulfa, trimipramine, voriconazole.
 
Azithromycin, citalopram, clomipramine, itraconazole, nortriptyline, paroxetine, solifenacin, tacrolimus
 
Fluoxetine, protriptyline, tamoxifen (Appendix J).

AE = Adverse event; BCRP = Breast cancer resistance protein; CYP = Cytochrome P450; ECG = Electrocardiogram.

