### J 2 Drugs Inhibiting CYP1A2 Metabolism that AstraZeneca Strongly Recommend are not Combined with Savolitinib

**Table J2 Drugs Inhibiting CYP1A2**

Contraindicated drugs	Withdrawal period prior to savolitinib start
Ciprofloxacin, Enoxacin, Clinafloxacin Fluvoxamine	2 weeks

CYP = Cytochrome P450.

This list is not intended to be exhaustive, and a similar restriction will apply to other agents

that are known to strongly inhibit CYP1A2 activity. Appropriate medical judgment is required. Please contact AstraZeneca with any queries you have on this issue.

Savolitinib is a weak inhibitor of Organic Anion Transporter Protein B1 and B3, and BCRP. The use of statins should be avoided as far as possible and if considered necessary, the patients should be given the lowest available dose and closely monitored for the effects of increased statin exposure.

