**Table J4 Drugs with a Known Risk of TdP**

Contraindicated drugs	Withdrawal period prior to osimertinib and/or savolitinib start b
Aclarubicin, anagrelide, ciprofloxacin, clarithromycin, cocaine, droperidol, erythromycin, levofloxacin, ondansetron, papaverine hydrochloride, procainamide, sulpiride, sultopride, terfenadine, terlipressin.	2 days
Cilostazol, cisapride, disopyramide, dofetilide, domperidone, flecainide, gatifloxacin, grepafloxacin, ibutilide, moxifloxacin, oxaliplatin, propofol, quinidine, roxithromycin, sevoflurane, sotalol, sparfloxacin, thioridazine	7 days
Azithromycin, bepridil, citalopram, chlorpromazine, dronedarone, escitalopram, fluconazole, halofantrine, haloperidol, levomepromazine, levostulpiride, mesoridazine	14 days
Donepezil, terodiline	3 weeks
Levomethadyl, methadone, pimozide	4 weeks
Arsenic trioxide a , ibogaine	6 weeks
Pentamidine	8 weeks
Astemizole, probucol, vandetanib	4 months
Amiodarone, chloroquine	1 year

a Estimated value as pharmacokinetics of arsenic trioxide has not been studied.

b Values determined from comprehensive review (internal to AstraZeneca) of each compound's PK half-life and determination of the wash-out period.

This list should be checked against the full and most current list presented in the CredibleMeds® website (<https://www.crediblemeds.org/>).

PK = pharmacokinetic; TdP = Torsades de Pointes.

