### J 5.4 Drugs that may Possibly Prolong QT Interval

The use of the following drugs is permitted (notwithstanding other exclusions and restrictions) provided the patient has been stable on therapy for the periods indicated.

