**Table J5 Drugs that may Prolong QT Interval**

Drug	Minimum treatment period on medication prior to osimertinib start
Alfuzosin, chloral hydrate, ciprofloxacin, dolasetron, foscarnet, galantamine, gemifloxacin, isridipine, ketoconazole, levofloxacin, mexiletine, nifedipine, octreotide, ofloxacin, ondansetron, quetiapine, ranolazine, telithromycin, tizanidine, vardenafil, venlafaxine, ziprasidone	2 days
Amantadine, amitriptyline, amoxapine, clozapine, doxepin, felbamate, flecainide, fluconazole, fosphenytoin, gatifloxacin, granisetron, imipramine, indapamide, lithium, moexipril/HCTZ, moxifloxacin, risperidone, roxithromycin, sertraline, trimethoprim-sulfa, trimipramine, voriconazole	7 days
Azithromycin, citalopram, clomipramine, itraconazole, nortriptyline, paroxetine, solifenacin, tacrolimus	14 days
Fluoxetine	5 weeks
Protriptyline	6 weeks
Tamoxifen	8 weeks

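### Ten drugs that Table J4 contraindicates for known torsades risk are permitted by Table J5 and Table 6 for patients already stable on them, and the only precedence wording is ambiguous

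*Supplement*

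**What the plan says.** **The ban.** Appendix J 5.1 covers drugs that the protocol classes as having a known torsades risk even when taken as recommended: "These drugs must have been discontinued prior to the start of administration of study intervention". They are not to be given with either study drug, nor for two weeks afterwards. Table J4 heads them as contraindicated and gives each a withdrawal period. Its first row begins "Aclarubicin, anagrelide, ciprofloxacin, clarithromycin, cocaine, droperidol, erythromycin, levofloxacin, ondansetron".

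**The permission.** Appendix J 5.4 says: "The use of the following drugs is permitted (notwithstanding other exclusions and restrictions) provided the patient has been stable on therapy". Table J5 then gives, under the column heading "Minimum treatment period on medication prior to osimertinib start", how long the patient must already have been taking each drug. Its first row includes "ciprofloxacin, dolasetron, foscarnet, galantamine, gemifloxacin, isridipine, ketoconazole, levofloxacin, mexiletine, nifedipine, octreotide, ofloxacin, ondansetron". Table 6 in Section 6.5 repeats the permission for the same drugs: "The use of the following drugs is permitted (notwithstanding other exclusions and restrictions) provided the patient has been stable on therapy for the periods indicated".

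**Other relevant text.**
- A separate row of Table 6 names drugs under the sentence "The following drugs are known to prolong QT interval or induce Torsades de Pointes and should not be combined with osimertinib". The same row tolerates QT-prolonging drugs that are essential to the patient's care, with more frequent ECGs.
- Exclusion criterion 3 (Section 5.2) bars concomitant drugs known both to prolong QT and to cause torsades. Section 5 allows no exceptions to the entry criteria.
- J 5.2 gives a similar stable-on-therapy permission, but only for the other torsades risk categories.
- J 5.3 tolerates essential QT-prolonging drugs whatever their category, with close ECG and electrolyte monitoring.
- J 5 tells sites to check current and intended drugs against the website that assigns the risk categories.
- Table J2 lists "Ciprofloxacin, Enoxacin, Clinafloxacin Fluvoxamine" as contraindicated, with two weeks off before savolitinib.

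**The concern.** A site cannot both stop a drug before study treatment and keep the patient on it because the patient is stable. Where one drug is on both lists, the protocol gives two opposite instructions, and the permissive one carries wording that seems to set the other aside. Section 6.5 sends the reader to Appendix J for drugs to avoid, but Appendix J holds both lists. A reader who stops at Table 6 sees only the permission for these drugs.

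This matters because QTc prolongation is a named risk of both study drugs in Table 3, and Appendix I 1.1 reports a positive thorough-QT study of savolitinib. A patient kept on a known-torsades drug would take it with one QT-prolonging study drug on savolitinib plus placebo, or with two on savolitinib plus osimertinib. Table J5 counts time up to the start of osimertinib. For a placebo-arm patient that start comes at cross-over, so the permission can be applied there as well as at first dose.

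**Working it through.** No sample size, power or error rate is involved. The check is a comparison of the printed lists, followed by a reading of the text for a rule of precedence.

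**Step 1: list sizes, adding the rows of each table.**
- Table J4: 15 + 18 + 12 + 2 + 3 + 2 + 1 + 3 + 2 = 58 drugs.
- Table J5: 22 + 22 + 8 + 1 + 1 + 1 = 55 drugs.
- Table 6, permitted row: the same 55, with one spelling variant.
- Table 6, row of drugs not to be combined with osimertinib: 25, all of them also in Table J4.

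**Step 2: drugs in both Table J4 and Table J5.** There are exactly ten.

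| Drug | Table J4: days off | Table J5: days on | Table 6 permitted row | Table 6 not-to-combine row |
|---|---|---|---|---|
| Azithromycin | 14 | 14 | yes | no |
| Ciprofloxacin | 2 | 2 | yes | no |
| Citalopram | 14 | 14 | yes | no |
| Flecainide | 7 | 7 | yes | no |
| Fluconazole | 14 | 7 | yes | no |
| Gatifloxacin | 7 | 7 | yes | no |
| Levofloxacin | 2 | 2 | yes | no |
| Moxifloxacin | 7 | 7 | yes | no |
| Ondansetron | 2 | 2 | yes | no |
| Roxithromycin | 7 | 7 | yes | no |

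The two day columns measure opposite things: time without the drug in Table J4 and time on it in Table J5. Their agreement in nine rows does not reconcile the tables.

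**Step 3: does another named list settle it?** Tables J1 and J3 contain none of the ten. Table J2 contains one, ciprofloxacin. Its two-week wash-out and the two-day wash-out in Table J4 are compatible, because the longer satisfies both. The conflict for ciprofloxacin is one permission against two bans. For the other nine, Table J4 is the only place that bans them by name.

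**Step 4: does the text rank the rules?** The notwithstanding clause in J 5.4 and Table 6 can be read in two ways.
- *As an override.* The permission beats every other exclusion and restriction. That undoes J 5.1 for these ten drugs and sets aside exclusion criterion 3.
- *As meaning subject to other restrictions.* J 5.1 and exclusion criterion 3 hold. Listing the ten in Table J5 and Table 6 is then a mistake.

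J 5.2 uses the same clause but confines it to other risk categories, and Section 5 admits no exceptions. Both favour the second reading. The literal sense of the words favours the first. The text needs correcting on either.

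**The case against.** The strict rule has solid support. Exclusion criterion 3 together with the no-exceptions rule gives a strong reading that a known-torsades drug bars entry whatever Table J5 says. A site that does the website check classifies each drug by category and should arrive at J 5.1. Several safeguards follow:
- the screening QTcF limits (470 msec for women, 450 msec for men) and the electrolyte exclusions;
- in Table 1, triplicate ECGs at screening, on Days 1, 8, 15 and 22 of Cycle 1, and on Day 1 of each later cycle;
- in Table I3, a review of concomitant drugs already at Grade 1 or 2 prolongation, and hold and stop rules above that.

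Known QT-prolonging drugs are in any case tolerated when essential, under J 5.3 and Table 6.

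Most of this stands, and it makes harm less likely. It does not repair the lists. Section 5 governs entry and not cross-over. The website check classifies a drug, but nothing says that its result cancels J 5.4. On-treatment ECGs act only after exposure has begun. The essential-use routes need a judgement of necessity, whereas J 5.4 asks only for prior stability.

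Three stronger readings go too far:
- *That nothing in the protocol addresses precedence.* The notwithstanding clause does. The fault is that it is ambiguous and, taken literally, favours the wrong list.
- *That all 33 Table J4 drugs missing from the Table 6 not-to-combine row (58 − 25) are left unguarded.* That row points to Appendix J, which bans them. Only the ten that are also permitted are in conflict.
- *That two days of an antibiotic are enough to qualify.* Table J5 gives a minimum period, and J 5.4 also requires the patient to be stable on therapy. Whether a short course would count is not stated.

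**Conclusion.** The conflict is real and limited to ten drugs. As written, J 5.4 and Table 6 would let a site start or cross over a patient who is taking a drug the protocol itself classes as a known torsades risk. The stricter rule is probably the intended one, but that is an inference from exclusion criterion 3, Section 5 and J 5.2, because no sentence states it unambiguously.

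The practical reach is small. Recruitment was stopped on 22 February 2022 and the current version dates from 9 May 2022, so new starts come only from patients already in pre-screening or screening, plus cross-over patients. The documents do not say how many patients take any of the ten drugs, so the number affected cannot be estimated. This is a safety-wording fault with no effect on endpoints, analysis or power. It is worth correcting because the interaction is a named risk and the correction is easy.

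**What to change.** 1. Delete the ten drugs from Table J5 and from the Table 6 row of drugs that may possibly prolong QT.
2. State in both places that Table J4, and the website's current known-risk category, override the stable-on-therapy permission.
3. Leave only the existing essential-use routes with close monitoring: J 5.3, and the Table 6 row on drugs prolonging QT.
4. For ciprofloxacin, refer to the longer two-week wash-out in Table J2.

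The cost is amendment wording and a letter to sites. No assessment is added. The downside is that a few patients taking one of these drugs would have to switch or wash out before starting study treatment or crossing over.

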**Table J4 Drugs with a Known Risk of TdP**

Contraindicated drugs	Withdrawal period prior to osimertinib and/or savolitinib start b
Aclarubicin, anagrelide, ciprofloxacin, clarithromycin, cocaine, droperidol, erythromycin, levofloxacin, ondansetron, papaverine hydrochloride, procainamide, sulpiride, sultopride, terfenadine, terlipressin.	2 days
Cilostazol, cisapride, disopyramide, dofetilide, domperidone, flecainide, gatifloxacin, grepafloxacin, ibutilide, moxifloxacin, oxaliplatin, propofol, quinidine, roxithromycin, sevoflurane, sotalol, sparfloxacin, thioridazine	7 days
Azithromycin, bepridil, citalopram, chlorpromazine, dronedarone, escitalopram, fluconazole, halofantrine, haloperidol, levomepromazine, levostulpiride, mesoridazine	14 days
Donepezil, terodiline	3 weeks
Levomethadyl, methadone, pimozide	4 weeks
Arsenic trioxide a , ibogaine	6 weeks
Pentamidine	8 weeks
Astemizole, probucol, vandetanib	4 months
Amiodarone, chloroquine	1 year

a Estimated value as pharmacokinetics of arsenic trioxide has not been studied.

b Values determined from comprehensive review (internal to AstraZeneca) of each compound's PK half-life and determination of the wash-out period.

This list should be checked against the full and most current list presented in the CredibleMeds® website (<https://www.crediblemeds.org/>).

PK = pharmacokinetic; TdP = Torsades de Pointes.

### J 5.2 Other TdP Risk Categories

Patients receiving drugs that prolong QT interval or may increase the risk of TdP from other TdP risk categories can be enrolled, notwithstanding other exclusions and restrictions, if these drugs are considered essential for patient management and the patient has been stable on therapy. Close monitoring of ECGs and electrolytes is recommended.

Patients with **congenital long QT syndrome** are excluded from this study.

### J 5.3 Guidance Regardless of TdP Risk Category

During study intervention and for a period of 2 weeks after discontinuing study intervention if it is considered essential for patient management to co-administer drugs known to prolong QTc interval, regardless of TdP risk category, close monitoring of ECGs and electrolytes is recommended.

### J 5.4 Drugs that may Possibly Prolong QT Interval

The use of the following drugs is permitted (notwithstanding other exclusions and restrictions) provided the patient has been stable on therapy for the periods indicated.

**Table J5 Drugs that may Prolong QT Interval**

Drug	Minimum treatment period on medication prior to osimertinib start
Alfuzosin, chloral hydrate, ciprofloxacin, dolasetron, foscarnet, galantamine, gemifloxacin, isridipine, ketoconazole, levofloxacin, mexiletine, nifedipine, octreotide, ofloxacin, ondansetron, quetiapine, ranolazine, telithromycin, tizanidine, vardenafil, venlafaxine, ziprasidone	2 days
Amantadine, amitriptyline, amoxapine, clozapine, doxepin, felbamate, flecainide, fluconazole, fosphenytoin, gatifloxacin, granisetron, imipramine, indapamide, lithium, moexipril/HCTZ, moxifloxacin, risperidone, roxithromycin, sertraline, trimethoprim-sulfa, trimipramine, voriconazole	7 days
Azithromycin, citalopram, clomipramine, itraconazole, nortriptyline, paroxetine, solifenacin, tacrolimus	14 days
Fluoxetine	5 weeks
Protriptyline	6 weeks
Tamoxifen	8 weeks

## Appendix K Abbreviations

Abbreviation or special term	Explanation
AE	Adverse event
ALP	Alkaline phosphatase
ALT	Alanine aminotransferase
ANCOVA	Analysis of covariance
AST	Aspartate aminotransferase
AUC	Area under the plasma concentration-time curve
AUC ss	Area under the plasma concentration-time curve at steady state
B	Blood
BCRP	Breast cancer resistance protein
BICR	Blinded independent central review
BP	Blood pressure
C 1h	Plasma concentration at 1 hour
C 3h	Plasma concentration at 3 hours
CEP7	Centromeric portion of chromosome 7
CI	Confidence interval
CL ss /F	Apparent clearance at steady state
CMH	Cochran–Mantel–Haenszel
COVID-19	Coronavirus 2019
C pre-dose	Plasma concentration pre-dose
CPQP	Clinical Pharmacology and Quantitative Pharmacology
CR	Complete response
CRO	Contract Research Organisation
CSP	Clinical Study Protocol
CSR	Clinical Study Report
C ssmax	Maximum plasma concentration at steady state
CT	Computed tomography
CTCAE	Common Terminology Criteria for Adverse Events
ctDNA	Circulating tumour DNA
CYP	Cytochrome P450
DCO	Data cut-off
DILI	Drug induced liver injury
DoR	Duration of response
ECG	Electrocardiogram

Abbreviation or special term	Explanation
ECHO	Echocardiogram
ECOG	Eastern Cooperative Oncology Group
eCRF	Electronic Case Report Form
EDC	Electronic data capture
EGFR	Epidermal growth factor receptor
EGFRm	Epidermal growth factor receptor mutation
EGFRm+	Epidermal growth factor receptor mutation positive
EM	Erythema multiforme
EMM	Erythema Multiforme Major
FAS	Full Analysis Set
FDA	US Food and Drug Administration
FDG-PET	Fluorodeoxyglucose-positron emission tomography
FFPE	Formalin-Fixed, Paraffin-Embedded
FISH	Fluorescence in situ hybridisation
FNA	Fine needle aspiration
GCP	Good Clinical Practice
HBsAg	Hepatitis B virus surface antigen
HBV	Hepatitis B virus
HCV	Hepatitis C virus
HDPE	High-density polyethylene
HGF	Hepatocyte growth factor
HIV	Human immunodeficiency virus
HL	Hy's Law
CCI	CCI
HR	Hazard ratio
IATA	International Airline Transportation Association
IB	Investigator's Brochure
ICF	Informed Consent Form
ICH	International Council for Harmonisation
IDMC	Independent data monitoring committee
IEC	Independent Ethics Committee
I-HAC	Independent Hepatic Assessment Committee
ILD	Interstitial lung disease
INR	International Normalisation Ratio
IO	Immune-oncology

Abbreviation or special term	Explanation
IRB	Institutional Review Board
IV	Intravenous
IVRS	Interactive Voice Response System
IWRS	Interactive Web Response System
LFT	Liver function test
LLN	Lower limit of normal
LMWH	Low molecular weight heparin
LVEF	Left ventricular ejection fraction
MedDRA	Medical Dictionary for Regulatory Activities
MET	Hepatocyte growth factor receptor
MRI	Magnetic resonance imaging
MUGA	Multi-gated acquisition
NCCN	National Comprehensive Cancer Network
NE	Not evaluable
NL	New lesions
NSCLC	Non-small cell lung cancer
NTL	Non-target lesions
NYHA	New York Heart Association
ORR	Objective response rate
OS	Overall survival
P	Plasma
PD	Progression of disease
PFS	Progression-free survival
PHL	Potential Hy's law
PK	Pharmacokinetics
PR	Partial response
Q6/8/12W	Every 6/8/12 weeks
QTc	Corrected QT interval
QTcF	QT interval corrected using Fridericia's formula
RECIST	Response Evaluation Criteria in Solid Tumours
CCI	CCI
S	Serum
SAE	Serious adverse event
SAP	Statistical Analysis Plan
SAS	Safety Analysis Set

Abbreviation or special term	Explanation
SD	Stable disease
SJS	Stevens-Johnson syndrome
SoAs	Schedule of activities
TBL	Total bilirubin
TdP	Torsades de Pointes
TKI	Tyrosine kinase inhibitor
TL	Target lesions
T ssmax	Time of maximum plasma concentration at steady state
U	Urine
ULN	Upper limit of normal
WHO	World Health Organization
WOCBP	Women of childbearing potential

## Appendix L Summary of Changes

### L 1 Amendment 1 (28 May 2021)

Section # and Name	Description of Change	Brief Rationale	Substantial/ Non-substantial
Appendix I: Dose Modifications for the Management of Adverse Events	Dose modification guidelines for osimertinib and savolitinib were updated. The main changes included addition of Table I1 (Study Treatment Dose Modification Instructions for Toxicities Related to Osimertinib and/or Savolitinib (excluding toxicities that require specific management guidelines), Table I2 (Toxicities that Require Permanent Discontinuation of Study Treatment), and Table I3 (Management of QTc Prolongation). Table I1 was created by combining information in previous Tables I2 and I4. Contents in previous Table I2 and Sections I2.4 are merged into new Table I2. Contents of previous Table I5 and Section I1.2 were merged to create new Table I3.	Dose modification guidelines updated in response to the FDA information request and in line with the prescribing label for osimertinib.	Substantial
Appendix I: Dose Modifications for the Management of Adverse Events	Instruction for recurrent Grade 3 savolitinib-related toxicities that resolved to baseline within 14 days of onset was removed.	Updated in line with most recent PSSR.	Substantial

